Patients meeting all inclusion criteria and no exclusion criteria will be invited to participate in the study. Patient eligibility for enrollment will be based on known information at the time of enrollment; information obtained at a later date may contradict this information but will not be considered a noncompliance with the study protocol. Patients will have the study procedures, risks and benefits explained to them and will have the opportunity to ask questions. Point of enrollment occurs when the patient is randomized into the study.

For patients who have not received any prenatal care or who, for any other reason, have not been assessed for abnormal placentation, it is recommended that an ultrasound be performed prior to study enrollment to assess the location of the placenta. Enrolled patients will be randomized 1:1 to treatment with the CRB plus Pitocin (Group A) or Pitocin alone (Group B). Randomization will utilize a computer generated randomization assignment that is stratified for parity, i.e., nulliparous and multiparous women will be accounted for in the randomization assignment. Approximately 200 pregnant women who meet the eligibility criteria will be enrolled into the study.

Both groups A and B will receive Pitocin in accordance with ACOG recommendations to be started within 90 minutes of study enrollment. Limit ambulation per site's standard of care following administration of Pitocin.

Patients randomized to Group A will undergo CRB placement within 90 minutes of study enrollment. Please reference the CRB IFU for a description of patient preparation and suggested instructions for use. In this study, the intrauterine balloon should be inflated with 60 cc of saline, and the vaginal balloon should be inflated with 30 cc of saline.

Pitocin Administration:

Pitocin will be administered in accordance with current ACOG recommendations and following institutional protocols. Details of Pitocin administration, including the maximum amount of Pitocin administered, amount of Pitocin administered at the time of delivery (prior to post-delivery bolus) and total amount of Pitocin infused, will be recorded for each patient. Providers are permitted to suspend Pitocin for periods of time at their discretion for maternal or fetal indications.

Intrapartum Procedure Management:

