The CRB will remain *in situ* for up to 12 hours or until it falls out of the vagina or when it is determined that the intrauterine balloon has descended past the cervix; please reference the IFU for a description of device removal. The removal of the CRB will have no impact on the use of Pitocin, its dosage, or its continued use. Those decisions will be made based on progress of labor and institutional standard of care, and in accordance with the Pitocin Administration guidelines described above.

All other aspects of labor management will be at the discretion of the primary obstetrical provider. Patients known to be group B streptococcus (GBS) positive will receive prophylaxis in accordance with CDC guidelines. A cervical exam including Bishop score should be completed at baseline (i.e., within 90 minutes of point of enrollment and prior to start of labor induction) and every 6 hours until delivery.

The use of fetal scalp electrodes and intrauterine pressure catheters will also be at the discretion of the obstetrical provider. Women will be able to choose analgesia or regional anesthesia depending on their preference. If a spontaneous delivery is not possible the ultimate decision to deliver by an operative vaginal procedure versus cesarean section will be made by the obstetrical provider using institutional and national criteria.

Uterine activity relative to contraction frequency and cervical change will be monitored along with fetal wellbeing (e.g., fetal heart tones assessment) per the discretion of the obstetrical provider.

Statistical Considerations:

Primary Effectiveness Hypothesis

The primary effectiveness endpoint, the time from start of labor induction to delivery, will be analyzed on a per-patient basis based on the intent-to-treat population. The primary effectiveness hypothesis is that patients treated with the CRB and Pitocin will experience decreased time from start of labor induction to delivery than patients treated with Pitocin alone.

$$H_0: t_{\text{CRB + PITOCIN}} > t_{\text{PITOCIN}}$$

$$H_1: t_{\text{CRB + PITOCIN}} \leq t_{\text{PITOCIN}}$$

Where:

$t_{\text{CRB + PITOCIN}}$: Mean time from start of labor induction to delivery in patients treated with the CRB and Pitocin

t_{PITOCIN} : Mean time from start of labor induction to delivery in patients treated with Pitocin alone

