The null hypothesis will be rejected in favor of the alternate hypothesis indicating that the treatment with the CRB and Pitocin is more effective than Pitocin alone at a p -value < 0.025 .

Primary Safety Hypothesis

The primary safety endpoint, the incidence of protocol-defined chorioamnionitis, will be analyzed on a per-patient basis based on the per-protocol population. The primary safety hypothesis is that patients treated with the CRB and Pitocin will experience non-inferior rates of protocol-defined chorioamnionitis than patients treated with Pitocin alone.

$$H_0: \pi_{\text{CRB + PITOCIN}} > \pi_{\text{PITOCIN}} + \delta$$

$$H_1: \pi_{\text{CRB + PITOCIN}} \leq \pi_{\text{PITOCIN}} + \delta$$

Where:

$\pi_{\text{CRB + PITOCIN}}$: Incidence of protocol-defined chorioamnionitis in patients treated with the CRB and Pitocin

π_{PITOCIN} : Incidence of protocol-defined chorioamnionitis in patients treated with Pitocin alone

δ : Margin of non-inferiority, set at 10% for this study

The null hypothesis will be rejected in favor of the alternate hypothesis indicating that the treatment with the CRB and Pitocin is as safe as Pitocin alone at a p -value < 0.025 .

Secondary Endpoints

The following secondary endpoints will be analyzed on a per-patient basis based on the per-protocol population:

- Incidence of failed induction,
- Incidence of cesarean section,
- Incidence of post-partum endometritis, and
- Incidence of cord prolapse.

For each outcome, the CRB and Pitocin will be compared to Pitocin alone, to assess for a significantly reduced rate. P -values will be adjusted using the Holm method controlling the family-wide Type I error rate at 0.05.

Additional Measures

The following additional measures will be reported:

- Time from PROM to delivery,
- Length of each stage of labor,
- Amount of Pitocin used,
- Incidence of post-partum hemorrhage,
- 1 minute, 5 minute, and 10 minute Apgar scores,

- Time from start of labor induction to delivery in patients with vaginal births,
- NICU admission rate,
- Total maternal hospital stay,
- Total newborn hospital stay,
- General cost analysis based on service utilization, and
- Maternal and newborn resource allocation.

Sample Size Calculations

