Cook intends to enroll 200 patients to account for those patients who might withdraw.

General Statistical Analyses

Statistical analyses will be performed using SAS® for Windows® (release 9.3 or higher) or other widely accepted statistical software. Clinically relevant baseline variables will be tabulated and compared between the treatment groups. Categorical variables will be assessed using appropriate contingency table analyses (chi-square test or Fisher's exact test) and logistic regression to assess the importance of covariates. Continuous variables will be tested using appropriate tests such as ANOVA, unpaired Student's t-test, or Wilcoxon rank-sum test, depending on variable distribution, and linear regression and repeated measure where appropriate. Survival analysis techniques such as Kaplan-Meier or Cox Proportional Hazards will be incorporated if censoring of data occurs.

Measures to be Taken to Avoid or Minimize Bias

This study is designed as a prospective, randomized, controlled clinical trial to minimize bias in both assigning patients to treatments and in analyzing the results.

Randomization

Assignment of patients to a treatment group will be by block randomization within each site and stratum. Sites will not be informed of the block size.

Missing Data

Due to the short-term follow-up of this study, a minimal amount of missing primary safety and effectiveness data is expected. Ten additional patients have been added to the required sample size to account for missing data. If necessary, multiple imputation will be used where the imputed values will be samples from the empirical distribution of the separate treatment groups.

The intent-to-treat population is defined as all patients who are randomized. The per-protocol population is defined as those patients who received the treatment as specified in their randomization.

Site-level Poolability

Poolability of data from multiple sites will be verified by examining the interaction between treatment arm and study site for the primary effectiveness and safety endpoints. Site-level poolability will be considered appropriate provided that these results are non-significant at the 0.05 level.

Adverse Event Definitions and Reporting:

Adverse events (AEs) are to be reported to the Data Coordinating Center using the appropriate case report form. In case of adverse device effects, completed forms will be submitted to the Data Coordinating Center as soon as possible upon knowledge of the event.

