As required by ICH-GCP the participant will give in writing her authorization that the study data may be given for review to the responsible authorities and that Sponsor representatives may view the participant's medical records for verification of clinical data. The ICF will be available in a language understandable to the participant.

If a protocol amendment is required, the ICF will be revised if applicable to reflect the changes to the protocol. After the ICF is revised, it must be reviewed and approved by the appropriate IRBs, and signed by all participants subsequently enrolled in the study. Upon request of the IRBs, the revised ICF may also be signed by those previously enrolled in the study.

Criteria and Procedures for Withdrawal:

A patient may decide to withdraw from the study at any time either before or after undergoing the procedure without prejudice or loss of care. The PI may also decide to withdraw the patient from the study at any time based on medical judgment. In these instances, the appropriate study visit and study termination data will be submitted to the Data Coordinating Center, and will include the reason why the patient has been withdrawn from the study.

Patients who withdraw consent after study enrollment will be followed until the time of their withdrawal. Any data collected on the patient up to the point of withdrawal may be used in the study. No patient will be removed from the study unless the patient has withdrawn his/her consent before treatment or no treatment was ever attempted.

Confidentiality:

All study findings and documents will be regarded as confidential. The investigator and members of his/her research team must not disclose such information without prior written approval from the Sponsor. The anonymity of participants must be maintained. Participants will be identified in the eCRF system and on other documents submitted to the Sponsor by their participant number, initials and/or birth date, not by name.

Publication:

At the conclusion of the study, the primary study outcomes will be published in a reputable scientific journal. Publication policy, rights and obligations for this study have been negotiated, detailed and defined in the study's contractual documents with the research sites and investigators.

Definitions:

Apgar score⁸ – An objective scoring system used to evaluate the condition of a newborn after birth.

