⁸ Apgar V, Holaday DA, James LS, Weisbrot IM, Berrien C. Evaluation of the newborn infant: second report. JAMA. 1958;168:1985-1988.

Score	Appearance (coloration)	Pulse (heart rate)	Grimace (reflex irritability)	Activity (muscle tone)	Respiration (breathing effort)
0	Blue or pale all over	Absent	No response	Limp	Absent
1	Blue or pale at extremities	< 100 bpm	Grimace or feeble cry	Weak, some movement	Weak or irregular
2	Pink all over	≥ 100 bpm	Cry or pull away	Active movement	Strong cry

Arrest of descent – Failure of the presenting fetal part to continue to descend during the second stage of labor despite uterine contractions and maternal effort (pushing).

Arrest of dilation – Failure of the cervix to progressively dilate despite active labor.

Bishop score⁹ – A scoring system used to help predict the success of labor induction. For this study, a standard Bishop score will be calculated using the scoring system below. No additional modifiers will be used in the calculation of the Bishop score.

Score	Dilatation	Effacement	Station	Position	Consistency
0	closed	0 – 30%	-3	Posterior	Firm
1	1 – 2 cm	40 – 50%	-2	Mid-position	Medium
2	3 – 4 cm	60 – 70%	-1, 0	Anterior	Soft
3	5+ cm	80+%	+1, +2	-	-

⁹ Bishop E. Pelvic scoring for elective induction. *Obstet Gynecol.* 1962;24:266-268.

Chorioamnionitis¹⁰ – A complication of pregnancy caused by bacterial infection of the fetal amnion and chorion membranes. A diagnosis of chorioamnionitis will include maternal fever $\geq 100.4^{\circ}\text{F}$ (38.0°C) plus at least two of the following symptoms with no other documented source of infection:

- Sustained maternal tachycardia with heart rate ≥ 100 bpm,
- Fetal tachycardia with fetal heart rate ≥ 160 bpm for at least 10 minutes,
- Foul smelling amniotic fluid,
- White blood cell (WBC) count $\geq 15,000$,
- C-reactive protein more than 2 mg/dL, or
- Uterine tenderness.

Cord prolapse – A condition that occurs when the umbilical cord descends alongside or beyond the fetal presenting part.

Dystocia – Pathologic or difficult labor, which may be caused by an obstruction or constriction of the birth passage or abnormal size, shape, position, or condition of the fetus.

Febrile – Temperature $\geq 100.4^{\circ}\text{F}$ (38.0°C).

Labor – A patient will be considered in labor if she is having regular, painful uterine contractions $\geq 6/\text{hr}$ resulting in progressive cervical effacement and dilatation.

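### Four secondary superiority tests are planned only in a per-protocol set that, on its plain wording, leaves out women whose CRB placement failed; they should be tested in all randomized women

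*Combined protocol and SAP*

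**What the plan says.** Under Secondary Endpoints, the analysis set for failed induction, cesarean, post-partum endometritis and cord prolapse is fixed: "The following secondary endpoints will be analyzed on a per-patient basis based on the per-protocol population". The tests look for benefit: "For each outcome, the CRB and Pitocin will be compared to Pitocin alone, to assess for a significantly reduced rate". Holm adjustment holds the family-wise error at 0.05. Sidedness is not stated.

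The population definitions stand under Missing Data. The intent-to-treat set is everyone randomized. For the other set: "The per-protocol population is defined as those patients who received the treatment as specified in their randomization".

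Under Study Procedure Initiation, enrollment is the moment of randomization, and the device step comes after it: "Patients randomized to Group A will undergo CRB placement within 90 minutes of study enrollment". Group B receives Pitocin only.

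The intent-to-treat set is named for one endpoint. Time from induction to delivery "will be analyzed on a per-patient basis based on the intent-to-treat population" (Primary Effectiveness Hypothesis). No all-randomized or sensitivity analysis of the four secondary endpoints appears anywhere.

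**The concern.** Failed placement happens after randomization and can happen only in Group A. On the plain wording, a woman in whom placement was tried without success did not receive CRB plus Pitocin, so she leaves the Group A denominator. Her counterpart in Group B, with the same cervix, stays in.

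The loss need not be random. The Definitions describe the Bishop score as "A scoring system used to help predict the success of labor induction", and a closed, posterior cervix scores 0 on dilatation and position. That such a cervix is also harder to place a balloon in is an inference; the protocol does not say so. If it is true, the women left out of Group A would tend to be those with the poorest prospects, and a lower cesarean or failed-induction rate could partly reflect their absence.

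There is also a safety side. If the cord prolapsed during a failed attempt and a cesarean followed, neither event would count in the secondary comparisons, although both relate to use of the device. And the main result on time to delivery could rest on different denominators from the cesarean rate reported beside it.

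**Working it through.** **1. The plan's own figures.** No sample size or power is stated for the secondary tests, so there is nothing to reproduce for them. The arm size comes from the primary effectiveness calculation: difference 539 − 416 = 123 minutes, SD 300, one-sided 0.025, power 0.80. The normal formula gives 2 × (1.960 + 0.842)² × (300/123)² ≈ 93.4, so 94 per group. The t-test version gives 94.35, so 95 per group and 190 in total, as stated. Enrolling 200 gives 100 per arm, used below.

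**2. The significance level.** With four tests, Holm starts at 0.05/4 = 0.0125. The level 0.025 = 0.05/2 is the third step, reached only after two rejections. I treat the tests as one-sided because the stated aim is a reduced rate; this is an assumption.

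**3. Assumptions not in the documents.** True cesarean rate 20% in both arms; a share s of Group A with failed placement; their cesarean rate k times that of the placed women. Group A overall is held at 20%, so the rate among placed women is

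r = 0.20 / [(1 − s) + s·k].

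With k = 2:
- s = 5%: r = 0.20/1.05 = 19.0%, n = 95.
- s = 10%: r = 0.20/1.10 = 18.2%, n = 90.

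With no device effect, the per-protocol comparison therefore starts 1.0 or 1.8 percentage points in favor of the CRB.

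**4. Chance of a false claim of fewer cesareans.** Sum Bin(a; n, r) × Bin(b; 100, 0.20) over all outcomes (a, b) that the test rejects, using the pooled chi-square or Fisher's exact test, both of which General Statistical Analyses permits.

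| Test, level | All randomized | Per-protocol, s = 5%, k = 2 | Per-protocol, s = 10%, k = 2 |
|---|---|---|---|
| Chi-square, 0.0125 | 1.23% | 1.90% | 2.70% |
| Fisher, 0.0125 | 0.81% | 1.28% | 1.71% |
| Chi-square, 0.025 | 2.57% | 3.59% | 5.04% |
| Fisher, 0.025 | 1.64% | 2.48% | 3.39% |

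**5. Cases that go the other way** (chi-square at 0.025, against 2.57% in all randomized women):
- Failed placements do better (k = 0.5): 2.00% (s = 5%) or 1.66% (s = 10%).
- Failed placements have the same rate (k = 1): 2.46% or 2.54%.
- 5% of Group B given a CRB and left out, k = 2, no loss in Group A: 1.67%.
- 5% left out of each arm, k = 2: 2.51%.

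**6. Rare endpoints** (chi-square at 0.0125, k = 2 or 3, s = 5% or 10%):
- Base rate 1%: per-protocol 0.02% to 0.03%, all randomized 0.13%.
- Base rate 3%: per-protocol 0.73% to 0.91%, all randomized 1.04%.

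At these rates the per-protocol error stays below 1.25%.

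**The case against.** The strongest reply is that the mechanism is assumed. The documents never mention failed placement and give no rate for it, and step 5 shows that plausible patterns cancel or reverse the bias. Group B women who deliver before Pitocin starts would also leave the per-protocol set, which the calculation does not model. All of this stands. It limits what can be said about size and direction, but it does not restore the protection of randomization.

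A second reply is that receipt of treatment may be meant to include an attempt, because the withdrawal section says: "No patient will be removed from the study unless the patient has withdrawn his/her consent before treatment or no treatment was ever attempted". That sentence governs removal from the study, not membership of the per-protocol set, and nothing links the two.

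A third is that baseline Bishop score is recorded, baseline variables are compared between groups, and logistic regression on covariates is foreseen. This could reveal a selective loss of unripe cervices. It would not undo it.

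Three stronger readings are tempting and are not supported:
- A reader might infer that a woman with a cord prolapse during a failed attempt disappears from every comparison. She stays in the time-to-delivery analysis, and the event is still reported as an adverse event.
- A reader might infer that all four tests are materially inflated. Step 6 shows otherwise for rare endpoints.
- A reader might extend the point to chorioamnionitis: "The primary safety endpoint, the incidence of protocol-defined chorioamnionitis, will be analyzed on a per-patient basis based on the per-protocol population". That is a non-inferiority test, where keeping all randomized women is not automatically the conservative choice. The point gives no reason to move it.

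**Conclusion.** The point holds as a matter of design. Four superiority tests rest only on a set defined by what happened after randomization, with one route of exclusion open to Group A alone, while the plan's own superiority test on time to delivery uses all randomized women. With no device effect, the all-randomized test keeps its error close to or below nominal whoever fails placement or crosses over; the per-protocol test does not.

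The size is modest and conditional. Under the step 3 assumptions with k = 2, the first-step error rises to about one and a half times the all-randomized value with 5% failed placements and to a little over twice with 10%. With Fisher's test and 5% failed, it is barely above the nominal 1.25%. The practical exposure is cesarean and perhaps failed induction. A reader might infer that the plan is biased toward the CRB; the documents support only that it is open to bias, in an unknown direction. Neither primary analysis is affected.

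**What to change.** Under Secondary Endpoints, name the intent-to-treat population, by assigned arm, as the set for all four Holm-adjusted tests, with per-protocol as a supportive analysis. Leave the primary chorioamnionitis test on the per-protocol set.

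Add one sentence to the withdrawal section: delivery outcomes are collected for every randomized woman, including those in whom no treatment was attempted, unless consent is withdrawn. This is needed because the present text allows such women to be removed. Women with an attempted placement already stay in the study, and Data Collection already covers their intrapartum events.

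The cost is a short text change, a little extra follow-up and some power. Assume cesarean is 20% with Pitocin alone, 10% in women with a placed CRB and 20% in unplaced Group A women. The all-randomized Group A rate is then 0.95 × 10% + 0.05 × 20% = 10.5% with 5% unplaced, or 0.90 × 10% + 0.10 × 20% = 11% with 10% unplaced. By chi-square at one-sided 0.025, power is 47% (all randomized) against 50% (per-protocol) with 5% unplaced, and 43% against 49% with 10%. If failed placements are rare, the loss is negligible.
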